7.2 MONITORING AND CLINICAL DATA REVIEW

The study site investigators are responsible for the initial evaluation and reporting of safety information at the participant level, and for alerting the protocol team if unexpected concerns arise. Sites are required to have detailed SOPs describing methods for social harms reporting to ensure that social harms are reported and managed in accordance with the protocol and for alerting the Protocol Team if unexpected concerns arise. Study participants will be provided a 24-hour telephone number and contact information and instructed to contact the study clinician to report any social harms they may experience. For life-threatening events, they will also be instructed to seek immediate emergency care. Where feasible and medically appropriate, participants will be encouraged to seek evaluation where the study clinician is based, and to request that the clinician be contacted upon their arrival.

The SDMC will prepare routine study conduct and social harms reports for the Study Monitoring Committee (SMC), which will meet by conference call approximately every 6 months. More frequent or *ad hoc* reviews may be conducted by the SMC as needed. A recommendation to stop the trial may be made by the SMC, if warranted.

7.3 SOCIAL IMPACT REPORTING

It is possible that participants' involvement in the study could become known to others, and that a social harm may result (i.e., because participants could be perceived as having HIV or at increased likelihood for HIV acquisition). For example, participants could be treated unfairly, or could have problems being accepted by their families and/or communities. Although self-identification as heterosexual is an inclusion criterion, it is possible that cisgender male participants may disclose having sex with other men or transgender individuals, including naming men as recent partners. Given the fact that homosexuality is illegal in Malawi, extensive care will be taken to preserve confidentiality and safety of all participants. All staff, including systems navigators, will be informed of the sensitive nature of all disclosed sexual activities and will be trained in the appropriate conduct of clinical research to treat all participants fairly and professionally. Reporting of any participant-reported homosexual activity is not required of research studies.

Research staff will be trained to recognize, collect, and report social impacts, and provide referrals for counseling and social service support, if necessary. Any social harm that is reported by the participant and judged by the IOR/designee to be serious or unexpected will be reported to the site's IRBs at least annually, or according to their individual requirements. Participants could also benefit from the study in various ways. Therefore,

both social harms and benefits due to participation in the study will be collected and reported on CRFs during regular visits. In the event that a participant reports a social harm, every effort will be made by study staff to provide appropriate care and counseling to the participant as necessary, and/or referral to appropriate resources for the safety of the participant. The site will provide such care and counseling in accordance with locally-available resources. While maintaining participant confidentiality, study staff may engage the CAB in exploring the social context surrounding instances of social impacts, to minimize the potential occurrence of such an impact.

8.0 STATISTICAL CONSIDERATIONS

8.1 REVIEW OF STUDY DESIGN

This is a single site, two-arm, randomized pilot study. Two-hundred eligible participants will be randomized to the intervention or standard of care arms in a 2:1 ratio.

Randomization will be stratified by age (15-25, >25), and a permuted blocks design will be used to ensure balanced treatment assignments within each stratum. Age-based stratification was selected due to expected differences in effect of intervention and base-case PrEP persistence among younger compared to older cisgender men. We have opted for a 2:1 randomization to facilitate evaluation of our acceptability outcomes, which are only examined among persons randomized to the intervention arm.

8.2 OBJECTIVES AND ENDPOINTS

Further details on how these endpoints are defined and measured are included in the statistical analysis plan (SAP). Of note, we aim to use validated instruments whenever feasible.

8.2.1 Primary Objective(s) and Endpoints

8.2.1.1 To assess the effect of a systems-navigator facilitated HIV prevention package on PrEP persistence among heterosexual cisgender men seeking STI clinical services in Lilongwe, Malawi at 26 weeks.

Consistent with this primary study objective, the following endpoint(s) will be assessed: Persistent PrEP use across all three modalities (LAI, daily oral, or event-driven PrEP), where persistence is defined as adherence to any PrEP modality through 26 weeks, comparing proportions in intervention and control arm participants.

- (LAI) receive on-time injections (+/- 7-day window for the first injection and 14-day window thereafter)
- (Daily Oral) have protective PrEP concentration detected at designated study follow-up visits, based on intraerythrocytic TFV-DP collected as DBS; TFV-DP concentrations associated with ≥ 4 doses/week will be classified as adherent.

- (Event-driven) self-reported PrEP adherence (2+1+1), in the past 30 days, assessed through self-report of PrEP use and sex acts at study follow-up visits, and intraerythrocytic TFV-DP concentrations.

8.2.1.2 To assess acceptability and barriers of implementing a systems-navigator delivered HIV prevention package among key stakeholders in the clinic and heterosexual cisgender men initiating PrEP at STI clinics.

Consistent with this primary study objective, the following endpoint(s) will be assessed among participants in the intervention arm only:

- Engagement with system navigators:
 - Overall: Proportion of intervention arm participants engaged by systems navigator within 7-days of enrollment visit (defined as any contact, i.e. text exchange, in-person communication)
 - Overall: Proportion of intervention arm participants engaged by systems navigators at least once after the initial engagement during the first 26 weeks following initiation of PrEP.
 - Overall: Proportion of intervention arm participants with attempted engagement by systems navigators at least once after the initial engagement during the first 26 weeks following initiation of PrEP.
 - Overall: Mean (standard error) number of contacts (text, telephone call, home visit, other) with intervention arm participants made with systems navigators (mean contacts per participant) during first 26 weeks following initiation of PrEP.
- Uptake of self-test/pill pack (“re-start” kit) among those to whom it is distributed (through end of study participation):
 - Proportion who self-report use of HIV self-test
 - Proportion who self-report use of PrEP pill pack
 - Proportion who self-report use of HIV self-test in conjunction with/prior to initiation of PrEP pill pack
- Acceptability and barriers among key stakeholders, including participants enrolled as seronegative PrEP initiators and other key stakeholders:
 - Acceptability based on quantitative surveys (participants enrolled as seronegative PrEP initiators only)
 - Perceived facilitators and barriers to implementation of the intervention will be assessed through individual semi-structured interviews.

8.2.2 Secondary Objective(s) and Endpoints

8.2.2.1 To assess the feasibility of a future randomized controlled trial.

Consistent with this secondary study objective, the following endpoint(s) will be assessed, considering all enrolled HIV seronegative participants:

- Calendar time to enroll 200 participants
- Proportion of participants retained at each [eligible] study visit
- Complete all study visits through 26 weeks, 39 weeks, and 52 weeks (among participants eligible for longer follow-up)
- Proportion of PrEP visits on the same day as study visits, by PrEP modality
- Proportion of participants completing 30-day TLFB at quarterly study visits
- Time to complete each study visit
- Additional time (at PrEP visits) engaging with systems navigators

8.2.3 Exploratory Objectives and Endpoints

8.2.3.1 To assess prevention-effective PrEP use among heterosexual cisgender men initiating PrEP at STI clinics

Prevention-effective PrEP use evaluates PrEP use in the context of ongoing HIV risk, exploring the alignment between periods with evidence of ongoing HIV risk and protective PrEP levels. This will be assessed for participants by evaluating self-reported HIV risk behaviors, observed incident STI or HIV, and PrEP use during quarterly study follow-up visits:

- Proportion of PrEP initiators with incident STI/HIV
- Proportion of PrEP initiators who report HIV risk during study follow-up, including self-reported sexual behaviors, and HIV status of partners
- Proportion of PrEP initiators who have target PrEP concentrations (oral) or on-time receipt (LAI) during periods of potential HIV risk based on incident HIV/STI, self-reported sexual behaviors, and HIV status of partners.
- Proportion of PrEP initiators who discontinue PrEP (based on self-report or medical record review)
- Proportion of sex acts with appropriate PrEP dosing (before and after each act) in 14- and 30-day recall periods, among PrEP initiators endorsing event-driven PrEP use

8.2.3.2 To assess PrEP modality preferences among heterosexual cisgender men initiating PrEP at STI clinics.

We will assess proportion of cisgender men selecting each of the available PrEP options at enrollment, and examine any changes in PrEP modality selection during study follow-up.

8.2.3.3 To assess the effect of a systems-navigator facilitated HIV prevention package on PrEP persistence among heterosexual cisgender men seeking STI clinical services in Lilongwe, Malawi, at 39 and 52 weeks.

Consistent with this exploratory objective, we will assess all PrEP use outcomes described in [Section 8.2.2](#) for subset of participants who are eligible for extended follow-up based on enrollment date, extending to 39 weeks or 52 weeks.

8.2.3.4 To quantify costs and resources necessary to develop and integrate a systems-navigator delivered HIV prevention package into an urban STI clinic, informing future cost-effectiveness model development.

Consistent with this exploratory study objective, the following endpoint(s) will be assessed:

- cost quantification following an ingredients-based micro-costing approach, including costs associated with training and time-and-motion evaluation of systems navigation activities including counseling and tracing.

8.2.3.5 To perform laboratory assessments that may include evaluation of factors related to HIV infection or other STIs; characterization of HIV in participants who acquire HIV; characterization of the host response to antiretroviral drugs; and evaluation of virologic, pharmacologic, or STI-based laboratory assays.

8.2.3.6 To evaluate event-driven PrEP drug concentrations within the context of TLFB reported PrEP use and sex acts.

8.2.3.7 To explore the perceived and experienced PrEP related stigma and potential influence of perceived gender norms on PrEP persistence among heterosexual cisgender men initiating PrEP at the STI clinic.
This exploratory objective will be assessed using a combination of quantitative surveys as well as the qualitative interviews with cisgender male participants.

8.3 SAMPLE SIZE

For our HIV seronegative PrEP initiation participant population, we expect to enroll approximately 200 heterosexual cisgender males. We assume 10% loss to follow-up through 26 weeks. As a pilot study, the sample size is chosen to provide reasonable precision for assessing the primary endpoints and informing future studies. We chose a

2:1 randomization to intervention and SOC to maximize our ability to assess acceptability of the intervention.

Based on previous studies, we expect persistent PrEP use under standard of care (SOC) is 40% at 26 weeks. The targeted difference in persistent PrEP use at 26 weeks between the intervention and the standard of care arm is 15%-35%. Table 1 gives the two-sided 95% confidence intervals for the true proportions of persistent PrEP use (a binary endpoint) separately for two arms. This is a pilot study seeking to rapidly evaluate indication of an effect signal that would suggest potential benefit of systems navigation to inform a future larger study. Our sample size, selected to quickly enroll and answer this important and timely knowledge gap, will be sufficient to identify a minimum detectable RD of 0.22 assuming 80% power and 5% alpha level, and RD of 0.25 assuming 90% power and 5% alpha level.

Table 2: 95% confidence intervals for the true proportions of persistent PrEP use at 26 weeks separately for two arms, given the total sample size of 200 and assuming 10% loss to follow-up (a working sample size of 180)

Proportion of persistent PrEP use under SOC	Proportion of persistent PrEP use under intervention with varying risk difference (RD)				
	RD=0.15	RD=0.2	RD=0.25	RD=0.3	RD=0.35
(0.28, 0.52)	(0.46, 0.64)	(0.51, 0.69)	(0.56, 0.74)	(0.62, 0.78)	(0.67, 0.83)

8.4 ACCRUAL AND RETENTION

A total of approximately 200 HIV seronegative PrEP initiating participants will be enrolled in approximately 39 weeks and followed for at least 26 weeks but up to 52 weeks. An overall retention rate of 90% will be targeted.

8.5 STATISTICAL ANALYSIS

8.5.1 Primary Analyses

Effect of intervention on persistent PrEP use

Comparison of persistent PrEP use will be performed on all enrolled participants during the first 26 weeks of study follow-up. Participants may choose to switch PrEP modalities during study follow-up; persistence to each modality will be assessed during the follow-up time when the participant reports using that modality, using a combination of self-report and clinic records. Only those who are retained on study at the end of 26 weeks will be considered to have reached the persistence endpoint. Data will be presented in a two-by-two table in which each participant is classified as persistent/non-persistent to PrEP. A Z-test based on asymptotic normality will be used to compare persistent PrEP between the intervention and the SOC arm.

Acceptability and barriers

For binary endpoints, the number will be tabulated, its specified proportion will be calculated, with variance calculated under binomial distribution. For continuous endpoints, its mean, median, standard deviation, quantiles and range will be calculated. Qualitative analyses are described separately ([Section 8.6](#))

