PrEP efficacy is associated with having adequate (effective or target) drug concentrations during periods of potential HIV exposure. Inadequate adherence to daily oral PrEP can lead to lower drug concentrations at anatomic sites of viral exposure, thus compromising PrEP effectiveness; the challenges associated with oral PrEP adherence may be mitigated by longer-acting agents, including LAI PrEP. Although LAI PrEP removes the need for daily dosing, timely injections are necessary to achieve and maintain target drug concentrations. Alternatively, so-called “on-demand” or “event-driven” PrEP, in which PrEP users take pills only around the time they have sex, may be protective against HIV acquisition and, depending on frequency of sex acts, could increase the interval between dosing compared to daily oral PrEP. However, data for use of this strategy has been mixed, and little is known about acceptability and effective use among heterosexual cisgender men. By triangulating timing of self-reported sex acts, self-reported event-driven PrEP use, and PrEP drugs levels collected at quarterly intervals, this study will be able to explore how these measures can be combined to better evaluate prevention-effective event-driven PrEP use among men.

Importantly, although a registered product approved for use in Malawi, and eventually expected to be available to cisgender men, LAI PrEP is not currently available at the time of this writing. It is expected to become an option for cisgender men during the proposed enrollment period. All three types of PrEP available (or to be available) to participants in this study (daily oral, “event-driven”, and LAI) are approved for use in Malawi. However, there are no prior studies documenting preference for, uptake of, or adherence to LAI PrEP (compared to daily oral or “event-driven”) among heterosexual cisgender men. Our preliminary work in this clinic suggests that between 50-60% of cisgender men may prefer injectable PrEP over pills, but this has only been examined in a hypothetical scenario to-date. This study will provide crucial information regarding preferences for PrEP modalities in this understudied population.

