Throughout the study design, we distinguish between PrEP visits and study visits. PrEP visits are conducted on a timeline determined by the MoH and should align with the modality of PrEP that a participant has selected. During a PrEP visit, the navigator will meet with the participant, discuss risk and PrEP use, and offer POC STI testing to inform the risk discussion. Navigators will conduct tracing activities for any missed PrEP visit, in accordance to PrEP-user stated preferences for tracing (see [Section 5.0](#)). Study visits, on the other hand, occur every 13 weeks regardless of PrEP modality, and are completed by study nurses. These visits include in-depth behavioral surveys and specimen collection. Participants receive a financial incentive to attend and complete the study visits, and these visits continue regardless of a participant’s decision to continue or discontinue PrEP use. Tracing for missed study visits will utilize study staff – these staff members are distinct from Systems Navigators, who only trace for missed PrEP visits in the intervention arm. This distinction and separation is crucial to inform our primary outcomes (effect of navigation on PrEP persistence) and avoid contamination of interpreting the PrEP use outcomes in the context of financial incentives that are external to the study intervention.

In-depth qualitative interviews will be conducted with a subset of cisgender men who initiate PrEP (approximately 20 at last study visit) and with other key stakeholders (approximately 15) including persons involved in provision of navigation, STI or HIV care or prevention (including clinic management or oversight), or development of HIV prevention policy or programming at local or national level. The purpose of these interviews is to explore facilitators and barriers to acceptability of the intervention components.

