9.1.3 Pharmacology

To address study objective 2.3.5, plasma and DBS samples for pharmacology testing will be collected throughout the study from all participants. Pharmacology testing will be performed at the HPTN LC or a laboratory designated by the HPTN LC. The primary pharmacologic assessments will be performed using assays that have been appropriately validated and approved. Results will not be returned to the study participants.

Interpretation of pharmacologic results, including pharmacokinetic modeling, will be led by the HPTN LC Pharmacology Core, in collaboration with other groups, as needed.

Stored plasma may also be tested for the presence of other antiretroviral drugs or other concomitant medications.

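### Does scoring oral PrEP users by the modality they report, under criteria of different strictness, make the primary comparison unreliable?

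*Protocol*

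**What the plan says.** Section 8.2.1.1 defines the primary endpoint as adherence to any of the three modalities through 26 weeks, with one criterion per modality. For daily oral PrEP, "TFV-DP concentrations associated with ≥ 4 doses/week will be classified as adherent". For event-driven PrEP, the criterion is 2+1+1 adherence "in the past 30 days, assessed through self-report of PrEP use and sex acts at study follow-up visits, and intraerythrocytic TFV-DP concentrations". For the injectable it is on-time injection.

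Section 8.5.1 says that "Participants may choose to switch PrEP modalities during study follow-up" and that persistence under each one "will be assessed during the follow-up time when the participant reports using that modality, using a combination of self-report and clinic records". Men not retained at 26 weeks cannot count as persistent. The arms are compared by one Z-test on a two-by-two table.

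Three other places bear on the point. Section 8.2 refers the reader to the SAP for how endpoints are defined and measured. Section 3.0 says that study visits "occur every 13 weeks regardless of PrEP modality, and are completed by study nurses", and that these staff are separate from the navigators. Section 1.2 says, of timing of acts, reported pill use and drug levels, that "this study will be able to explore how these measures can be combined to better evaluate prevention-effective event-driven PrEP use among men".

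**The concern.** The trial is open-label, modality can change after randomisation, and the modality a man reports helps decide which criterion he must meet. One oral criterion is a laboratory threshold. The other begins with his own account of pills and sex acts. The same tablet intake can therefore fail as daily use and pass as event-driven use.

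Only the intervention arm has navigators who counsel on PrEP use, so one can imagine the event-driven label, or favourable reporting under it, being commoner there. That could create an apparent effect. If it were equal in both arms, it could dilute a real one. The single two-by-two table would not show either. Section 1.2 adds to the worry, because it can be read as saying that the event-driven measure is still being worked out.

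**Working it through.** **1. The plan's own figure.** Inputs from section 8.3: standard-of-care persistence 0.40, 200 men at 2:1, 10% loss, hence 60 and 120; alpha 5%, taken as two-sided. At a risk difference (RD) of 0.22:

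- pooled proportion = (60 × 0.40 + 120 × 0.62)/180 = 0.547
- null SE = √(0.547 × 0.453 × (1/60 + 1/120)) = 0.0787
- alternative SE = √(0.24/60 + 0.2356/120) = 0.0772
- power = Φ((0.22 − 1.96 × 0.0787)/0.0772) = Φ(0.85) = 0.80

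RD 0.25 gives 0.895. Both stated figures (80% and 90%) reproduce.

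**2. Do the two oral criteria diverge at the same intake?** Four doses a week is 4 × 30/7 = 17.1 tablets in 30 days. One 2+1+1 course is 4 tablets. With separate courses and one tablet per dose:

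| Separate acts in 30 days | Tablets | Tablets per week |
|---|---|---|
| 1 | 4 | 0.93 |
| 2 | 8 | 1.87 |
| 3 | 12 | 2.80 |
| 4 | 16 | 3.73 |
| 5 | 20 | 4.67 |

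So a correct event-driven user with 1 to 4 acts falls below the daily cut-off. The divergence is real.

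**3. Is the divergence a misclassification?** Not under the stated endpoint. Persistence is adherence to the modality used. A man who covers every act with 2+1+1 has adhered to his, and scoring him persistent is the intended result. The table shows that the regimens need different numbers of tablets. A wrong score requires a false report of acts or pills, or a false label. Self-report is not the only input to either: the event-driven criterion also names TFV-DP, and the label also draws on clinic records. How strictly those inputs bind depends on details that section 8.2 assigns to the SAP.

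**4. How large could the effect be?** Every rate here is assumed; the protocol gives no event-driven share. All figures are exact binomial with a pooled Z.

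*Equal in both arms, 60/120.* If a fraction m of non-persistent men is wrongly rescored, p0 = 0.40 + 0.60m, p1 = 0.62 + 0.38m and RD = 0.22(1 − m).

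| m | RD | Power |
|---|---|---|
| 0 | 0.22 | 0.80 |
| 0.1 | 0.20 | 0.72 |
| 0.2 | 0.18 | 0.64 |
| 0.3 | 0.15 | 0.55 |

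The false-positive rate stays at about 5%.

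*Intervention arm only, all enrolled (67/133), no true effect.* Retained non-persistent men are 0.90 − 0.40 = 0.50 of an arm, so p1 = 0.40 + 0.50s. Rescoring s = 0.1 or 0.2 gives a false RD of 0.05 or 0.10 and rejection in 10% or 26% of trials. A false RD of 0.22 needs s = 0.22/0.50 = 44%.

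**5. Would a drug-level-only analysis settle it?** Suppose every oral user were held to the daily cut-off, and nobody misreports. Let q be the share of truly persistent men who are correct event-driven users below that cut-off. Simulation at 60/120, 0.40 v 0.62:

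| q, standard of care | q, intervention | Power, drug level only | Significant primary results that turn non-significant |
|---|---|---|---|
| 10% | 10% | 0.72 | 13% |
| 20% | 20% | 0.62 | 26% |
| 30% | 30% | 0.52 | 37% |
| 10% | 20% | 0.41 | 49% |

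With entirely honest reporting the two analyses often disagree, because the threshold changed. Such disagreement cannot be read as dependence on self-report. Nor is the alternative free of self-report: deciding whether a man was on oral or injectable PrEP at a given time still uses his account and clinic records.

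**The case for a change.** The best case for the concern is that it rests on what the protocol itself fixes, not on what the SAP may add. The reported-modality rule and the unequal criteria are in the text. A SAP cut-off for event-driven use low enough to admit men with few acts would still differ from the daily one; a cut-off equal to it would fail them. Navigator counselling and restart kits exist in one arm only, so a difference in labels between arms is plausible. The exploratory drug-level endpoints in 8.2.3.1 and 8.2.3.6 do not fill the gap, since they are tied to risk periods or to reported acts. And a check looks cheap, because "plasma and DBS samples for pharmacology testing will be collected throughout the study from all participants".

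Part of this stands. The protocol gives neither an event-driven TFV-DP cut-off nor a rule for conflict between self-report and clinic records, and both matter. But these are measurement details of the kind a protocol commonly leaves to the SAP, and so is any supportive analysis. That some label dependence survives any cut-off is a consequence of admitting regimens with different dosing, not a mistake in scoring them. Difference between arms remains unshown, and the outcome visits are run by staff separate from the navigators. The remark in section 1.2 concerns prevention-effective event-driven use, which belongs to exploratory objectives 2.3.1 and 2.3.6; the measures overlap with the primary criterion, but the remark does not say that the primary rule is unsettled. Cheap samples do not rescue a comparison whose result would be ambiguous.

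**Conclusion.** The concern does not hold against this protocol. Different criteria for different regimens follow directly from defining persistence as adherence to the modality used, and the men who pass as event-driven but would fail as daily users include those the definition is meant to count. The power loss (80% down to 72%, 64% or 55%) and the false-positive rates (10% or 26%) are correct arithmetic, but they rest on assumed rescoring rates and on treating every rescored man as truly non-persistent, which the endpoint definition does not support. Whether a label could wrongly change a score turns on the event-driven cut-off and the precedence of records, which belong to the SAP, not shown here. This conclusion assumes that the SAP does specify them; it does not claim that self-reported event-driven adherence is accurate.

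### Randomisation is stratified by age because age is expected to matter, but the primary Z-test ignores the strata; if age is clearly prognostic the test is conservative and gives up a little power

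*Protocol*

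**What the plan says.** On design, section 8.1 states: "Randomization will be stratified by age (15-25, >25), and a permuted blocks design will be used to ensure balanced treatment assignments within each stratum". The reason follows: "Age-based stratification was selected due to expected differences in effect of intervention and base-case PrEP persistence among younger compared to older cisgender men". Allocation is 2:1 in favour of the intervention, with 200 participants.

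On analysis, section 8.5.1 states: "Data will be presented in a two-by-two table in which each participant is classified as persistent/non-persistent to PrEP". It then names the test: "A Z-test based on asymptotic normality will be used to compare persistent PrEP between the intervention and the SOC arm". Neither sentence mentions age, and the form of the variance (pooled or unpooled) is not given.

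On size, section 8.3 expects 40% persistence under standard of care (SOC) and says the sample "will be sufficient to identify a minimum detectable RD of 0.22 assuming 80% power and 5% alpha level", with 0.25 at 90% power. The working number is 180 after 10% loss. The protocol gives neither the expected share of men aged 15-25 nor the expected age gap in persistence.

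**The concern.** The protocol treats age as important enough to control in the allocation, then leaves it out of the primary test. Permuted blocks within strata keep the arms close to 2:1 in each age group, so age differences contribute almost nothing to the variability of the arm difference. The crude binomial standard error does not know this and keeps the between-age variance. If age is prognostic, the standard error is too large, the interval too wide and the p-value too big.

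Efficiency is at stake, not validity. This is a pilot looking for a signal with about 60 evaluable SOC participants, so precision that can be recovered from data already collected is worth having.

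**Working it through.** **Inputs from the protocol.** 2:1 allocation; SOC persistence 0.40; 180 evaluable, hence 60 SOC and 120 intervention; alpha 5%. Sidedness is not stated for the test; two-sided reproduces the plan's figures.

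**Assumptions.** SOC rates in the two age groups of 0.40 − g/2 and 0.40 + g/2, with gap g from 0 to 0.3; equal strata unless stated; the same RD in both strata unless stated.

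**1. The plan's own figure.** At RD 0.22 the pooled rate is (0.40 + 2 × 0.62)/3 = 0.5467.
- Null SE = √[0.5467 × 0.4533 × (1/60 + 1/120)] = 0.0787.
- Alternative SE = √[0.40 × 0.60/60 + 0.62 × 0.38/120] = 0.0772.
- Power = Φ[(0.22 − 1.96 × 0.0787)/0.0772] = Φ(0.85) = 80.3%.

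The same calculation at RD 0.25 gives 89.5%. Solving for RD gives 0.219 and 0.252. The stated 0.22 and 0.25 are reproduced, and they come from an unstratified test.

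**2. True error rate of the crude test.** Under the null with equal strata, the crude variance is 0.24 × (1/60 + 1/120) = 0.24 × 0.025 = 0.0060. The actual variance under stratified allocation is (0.24 − g²/4) × 0.025. The ratio is 1 − g²/0.96, and the true two-sided error is 2[1 − Φ(1.96/√ratio)].

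| Gap g | Ratio | 1.96/√ratio | True alpha, formula | Simulated: pooled Z / unpooled Z / CMH (N=180) |
|---|---|---|---|---|
| 0 | 1.000 | 1.960 | 5.0% | 5.0% / 5.3% / 4.9% |
| 0.1 | 0.990 | 1.970 | 4.9% | 4.8% / 5.2% / 4.9% |
| 0.2 | 0.958 | 2.002 | 4.5% | 4.5% / 4.9% / 5.0% |
| 0.3 | 0.906 | 2.059 | 4.0% | 3.9% / 4.2% / 5.0% |

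The simulations used 400,000 trials per setting, 2:1 fixed within each stratum, and CMH without continuity correction. A separate simulation with random stratum sizes and blocks of six (block size assumed) gave the same pattern.

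**3. Power at RD 0.20, pooled Z to CMH, same simulations.**

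| Gap g | N=180 | N=200 |
|---|---|---|
| 0.1 | 72.6% to 72.6% | 76.9% to 76.9% |
| 0.2 | 72.8% to 73.7% | 77.2% to 78.1% |
| 0.3 | 73.4% to 76.5% | 77.8% to 80.5% |

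Both sizes are shown because section 8.5.1 analyses all enrolled participants and counts only those retained as persistent. With 70/30 or 30/70 strata, pooled-Z alpha is 4.5-4.8% at gap 0.2 and 4.1-4.3% at gap 0.3. The corresponding power losses are 0.6-1.5 and 2.2-2.6 points.

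**4. Power at the planned RD of 0.22, N=180.** For gap 0.3 the alternative SE under stratified allocation is 0.0735. The null SE is 0.0787 crude and 0.0751 stratified.
- Crude: Φ[(0.22 − 1.96 × 0.0787)/0.0735] = 81.4%.
- Stratified: Φ[(0.22 − 1.96 × 0.0751)/0.0735] = 83.9%.

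Over all gaps from 0 to 0.3 and all stratum splits simulated, the crude pooled test kept 80.3% to 81.5%.

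**5. Interval width at RD 0.15, N=180.** The half-width is 1.96 × √[(0.24 − g²/4)/60 + (0.2475 − g²/4)/120] for the stratified interval, and the same with g = 0 for the crude one.
- Crude: 0.153.
- Stratified, gap 0.2: 0.149.
- Stratified, gap 0.3: 0.145.

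Simulated average Wald half-widths were 0.152, 0.147 and 0.143. About 0.002 of that narrowing is small-sample bias in the stratified variance, so the formula values are the fairer measure of gain.

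**The case against.** The strongest reply is that nothing here is wrong: the crude Z-test is valid, matches the sample-size calculation and keeps at least 80% power at RD 0.22. All of that stands, and it caps the importance of the point.

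Three narrower objections also have force.

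- **The gap is assumed.** A gain of about 3 points needs SOC persistence of, say, 25% against 55%, and the protocol claims no gap of that size. At a gap of 0.1 there is nothing to gain.
- **The effect may also differ by age**, as section 8.1 itself expects, whereas the power figures above use a constant RD. With N=180, equal strata and mean RD 0.20, SOC rates of 0.30/0.50 with RDs of 0.30/0.10 give 72.8% for both tests. SOC rates of 0.25/0.55 with the same RDs give 73.0% and 73.5%. The reverse pattern (0.30/0.50 with RDs of 0.10/0.30) gives 73.3% and 77.0%. So the gain ranges from about nil to nearly 4 points, and none of these scenarios shows a material loss.
- **The variance is unspecified.** With an unpooled variance the crude test starts slightly above 5% and is clearly conservative only near a gap of 0.3.

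It can also be said that stratum handling belongs in the SAP, which is not at hand, and that a stratum-weighted difference over its standard error is a Z-test too. But section 8.5.1 names both table and test, and its plain reading is unstratified. The SAP reference in section 8.2 concerns how endpoints are defined and measured. An SAP that stratified the primary test would depart from the plain reading of the protocol sentence.

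**Conclusion.** The point holds as a conditional and minor one. If SOC persistence differs by 20 to 30 percentage points between the age groups, the pooled Z-test runs at about 3.9-4.8% instead of 5%. With a constant RD of 0.20 it then gives up roughly 1 to 3 power points against an age-stratified test. If age is weakly prognostic, the difference is negligible.

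The point estimate hardly moves, because with 2:1 allocation in each stratum the crude and stratum-weighted RDs nearly coincide. Type I error is not materially inflated, and the detectable differences in section 8.3 stand. The age gap and stratum shares are assumptions throughout; the power gain also depends on how the effect varies with age.

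**What to change.** In section 8.5.1, replace the Z-test sentence with wording such as:

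> Persistence at 26 weeks will be compared between arms with a two-sided 5% Cochran-Mantel-Haenszel test stratified by randomization age group (15-25, >25). The primary estimate is the Mantel-Haenszel (stratum-weighted) risk difference with its 95% CI. Risk differences by age group are descriptive.

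The two-by-two table can stay as the data display. The new wording also states the sidedness, removes the open choice of pooled or unpooled variance, and shows results by age group, where section 8.1 expects the effect to differ. The cost is this change of wording and a few lines of code; no new data and no change in sample size are needed.
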